## 2) Objectives

The objective of this study is to conduct a cluster randomized controlled trial to test the efficacy of a psychosocial intervention to support Alzheimer's family caregivers in Vietnam. The cluster RCT will test the hypothesis that family caregivers who receive the intervention will show lower psychological distress and lower caregiver burden compared with those in the control group (primary outcomes). In addition, we will conduct secondary analyses to examine whether intervention group has lower perceived stress and somatic symptoms.

Exploratory analyses will be conducted to determine if intervention effects are mediated by caregiver self-efficacy or knowledge gain.

## 3) Background

Low and middle-income countries (LMIC) such as Vietnam are undergoing a dramatic demographic transition that will result in a substantial increase in the number of older adults, including those afflicted with Alzheimer's disease and related dementias, over the next several decades. Dementia is among the most disabling and costly neurodegenerative brain diseases. Strengthening LMIC capacity to support family caregivers of persons with dementia through low-cost and sustainable non-pharmacological approaches, such as education and skill-building to deal with difficult behaviors, is vital to avoid costly and ineffective alternatives such as psychotropic medications or institutionalization, and to reduce caregiver burdens and depression. While evidence-based non-pharmacological treatments exist in high income countries (HIC), these interventions have not been adapted for use in Vietnam and other LMIC.

This project addresses these gaps by testing a community-based and culturally adapted behavioral family caregiver intervention for use in Vietnam. The intervention has several components (psychoeducation, stress reduction, skill-building) and is designed to reduce caregiver stress and burden. This project also builds directly on a pilot cluster RCT that found evidence for feasibility and preliminary efficacy of the intervention.

## 4) Inclusion and Exclusion Criteria

To be eligible for the cluster RCT, the family member will need to be the identified adult (age 18 and above) primary caregiver (i.e., the person spending who provides the most time day-to-day providing care) to an older adult with dementia who is living in the community. In the event that the primary caregiver

**PROTOCOL TITLE: Cluster Randomized Controlled Trial to Test the Efficacy of a Psychosocial Intervention (REACH VN) to Support Alzheimer's Family Caregivers in Vietnam**

is not available to participate, an alternate family member who providing substantial (i.e., at least 4 hours/day) of care to the older adult with dementia will be eligible. Caregivers will need to score  $\geq 6$  on the Zarit Burden Inventory 4-item version. All participants will be living in designated clusters in Hai Duong, Vietnam. To be eligible, clusters will have a minimum of 5 participants and a maximum of 15 participants. Clusters will be defined as geographic areas serving local health stations.

The final sample for the cluster RCT will be 350 family caregivers of persons diagnosed with dementia (175 in the active intervention and 175 in the control group). The RCT will exclude:

- Caregivers who are unable to consent
- Individuals who are not yet adults (infants, children, teenagers)
- Prisoners

## **5) Study Timelines**

- We will begin recruitment in August of 2020.
- We will complete recruitment by September of 2023.
- We will complete all data collection and intervention activities by March of 2024.
- We will complete preliminary analysis of the data by August of 2024.

## **6) Study Endpoints**

This is a time-limited intervention lasting up to 3 months with independent assessment of outcomes at baseline, 3 months, and 6 months.

## **7) Procedures Involved**

The study will be conducted in two districts in Hai Duong, a province located near Hanoi, Vietnam. Clusters within both districts will be defined as geographic areas served by local health clinics (commune health stations). In collaboration with commune health stations, community-based screening will be conducted to identify Alzheimer's family caregivers residing in the designated clusters who will then be invited to participate in the study. Clusters will be randomly assigned to either the intervention (approximately 21 clusters, 175 caregivers) or to the enhanced control condition (approximately 21 clusters, 175 caregivers).

Staff from the National Geriatric Hospital and Hai Duong Provincial Hospital will train local staff (e.g., village health workers) to identify persons at high risk for dementia from their caseloads, including those with a history of significant memory problems, behavioral issues and evidence of functional decline.

Research staff from local health clinics will contact potential participants by phone, provide information about the project, and invite them to participate in

**PROTOCOL TITLE: Cluster Randomized Controlled Trial to Test the Efficacy of a Psychosocial Intervention (REACH VN) to Support Alzheimer's Family Caregivers in Vietnam**

screening to determine their eligibility. Verbal consent will be obtained from the older adult and a family member prior to screening by research staff. Those who consent to participate in the screening will undergo an assessment including a brief neurological exam, bedside cognitive testing and dementia stage using standard instruments, including the Mini-Cog, NPI-Q and CDR. Once an older adult has been determined to meet criteria for dementia (i.e, CDR $\geq$ 1), we will identify the adult family member providing the most day-to-day care and invite them to participate in the study and obtain verbal consent. Because of the minimal risk of both screening and behavioral intervention, verbal consent will be obtained for both.

Family caregivers in the intervention will receive a manualized intervention that will consist of 3-6 one-hour sessions with a trained staff (e.g. nurse, social worker, or community health worker) who has been certified to deliver the intervention. The sessions will be administered at home (or other setting of the subject's choice such as a clinic) or by phone and include several components, including psychoeducation, stress reduction, skill-building. The intervention will be tailored to the needs and preferences of the caregiver. As part of the intervention, participants will receive a caregiver notebook with information about dementia and management of common problems. Participants in the control clusters will receive a single session in which they will receive education about Alzheimer's disease including written materials.

Outcomes will be assessed by research staff from the Institute of Population Health and Development who are masked to allocation. Participants in both clusters will be assessed at baseline, 3 months, and 6 months to assess primary and secondary outcomes using standardized instruments, including the PHQ-4, Zarit Burden Interview-12, Perceived Stress Scale-10, PHQ-15 (a somatic symptoms scale). In addition, we will assess two different potential mediators using the Caregiving Self-Efficacy Scale and Dementia Knowledge Scale. Assessments will be conducted by research staff who are masked to allocation.

The interventionists will follow a manual (Interventionist Manual) that includes scripts, detailed descriptions of the goals for each session, and standardized forms. The interventionists will provide the caregivers with a detailed notebook with helpful caregiving information (Caregiver Notebook).

For training purposes only and quality control of the intervention, we will audio record a subsample of the intervention sessions. These audio recordings will be stored securely and will not be linked to participant's name or other identifying information. These will not be used for research purposes. The recordings will be reviewed within 6 months and then destroyed. Participants may continue their participation in this study without consenting to these recordings and having any impact on their participation.

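### Section 7 does not secure that a commune's arm stays hidden until its caregivers are enrolled; separately, and less important, the two districts are neither balanced nor modelled

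*Protocol*

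**What the plan says.** **Allocation.** Protocol section 7 states: "Clusters will be randomly assigned to either the intervention (approximately 21 clusters, 175 caregivers) or to the enhanced control condition". It gives no method of generating the sequence, no holder, no time of release and no balancing factor.

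**Recruitment.** The same section says hospital staff "will train local staff (e.g., village health workers) to identify persons at high risk for dementia from their caseloads". Then "Research staff from local health clinics will contact potential participants by phone" and invite them to screening. Entry requires a CDR of at least 1 (section 7) and a Zarit 4-item score of at least 6 (section 4). Section 4 adds: "To be eligible, clusters will have a minimum of 5 participants and a maximum of 15 participants".

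**Delivery and masking.** Sessions are given by "trained staff (e.g. nurse, social worker, or community health worker) who has been certified to deliver the intervention". Masking to allocation is stated for outcome assessors only.

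**Timing.** Recruitment is planned from August 2020. Section 5 then says "We will complete recruitment by September of 2023" and "We will complete all data collection and intervention activities by March of 2024".

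**District.** "The study will be conducted in two districts in Hai Duong", with clusters in both. The SAP model has the baseline value as a covariate and a random intercept for participants within communes. The adjusted models add caregiver and patient characteristics. District is not named anywhere in the SAP.

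**The concern.** In a cluster trial, a whole commune has one arm. If the people choosing and telephoning caregivers know that arm, who is approached, and who agrees, can differ between arms. Masked outcome assessment does nothing about this, because the difference is built in before the first assessment. Covariate adjustment removes only the part that the measured covariates capture. The primary outcomes are self-reported distress and burden, and one entry criterion is a self-reported burden score, so differential enrolment could act on the quantities being compared.

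District is a different kind of issue. With unstratified assignment, one arm can by chance draw more communes from one district. That is not bias. It adds noise to the arm contrast that stratification with a matching model term would take out.

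**Working it through.** **1. The plan's own figures.** 175 + 175 = 350 caregivers; 21 + 21 = 42 communes; 350/42 = 8.33 per commune, inside the limits of 5 and 15. These agree.

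**2. Is concealment until enrolment secured?** There is no calculation to do; the passages are set side by side.

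- *Pointing to enrolment first:* in section 7, community screening and invitation are described just before the allocation sentence. In section 4, a cluster qualifies only if it has 5–15 participants, which is most naturally checked before assignment.
- *Not settling it:* the detailed account of case-finding, telephoning, screening and consent comes after the allocation sentence, so the order of the text can be read both ways. The size rule does not say when participants are counted.
- *Who has discretion:* local staff choose from their own caseloads and clinic-based staff make the calls. No masking is stated for either.
- *What limits discretion:* the CDR and Zarit thresholds. The Zarit score is self-reported, so this limit is partial.

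No passage gives the difference in enrolment that would follow if an arm were known, so no size or direction is calculated.

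**3. District: chance of imbalance.** The split of communes between districts is not given, so three are assumed. With *D* communes in the smaller district and 21 of 42 drawn for the intervention, the number *k* drawn from that district is hypergeometric(42, *D*, 21), and the difference between arms is |2*k* − *D*|.

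| Assumed split | P(difference of 5 or more communes) |
|---|---|
| 21:21 | 0.217 |
| 14:28 | 0.100 |
| 10:32 | 0.067 |

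(When *D* is even only even differences can occur, so 5 or more then means 6 or more.)

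**4. District: precision.** Assumptions: gap between districts *G* = 0.2–0.4 SD at baseline and follow-up, slope on baseline *b* = 0.5, within-district ICC 0.01–0.10. With *p* the share of communes in one district:

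- district variance left after the baseline covariate: *d* = [*G*(1 − *b*)]² × *p*(1 − *p*)
- other variance of a commune mean: *v* = (1 − *b*²) × [ICC + (1 − ICC)/8.33]
- share of variance removed by stratifying with a district term: *d*/(*v* + *d*)

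*Largest case* (21:21, *G* = 0.4, ICC 0.01): *d* = 0.04 × 0.25 = 0.0100; *v* = 0.75 × (0.01 + 0.1188) = 0.0966; share = 0.0100/0.1066 = 9.4%.

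*Smallest case* (10:32, *G* = 0.2, ICC 0.10): *p*(1 − *p*) = (10/42)(32/42) = 0.1814; *d* = 0.01 × 0.1814 = 0.0018; *v* = 0.75 × (0.10 + 0.108) = 0.156; share = 0.0018/0.1578 = 1.1%.

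In standard error, 1 − √(1 − share) gives 4.8% and 0.6%. If *G* = 0 the gain is nil.

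A district term without stratification gains less. A simulation on commune means (20,000 runs, 21:21, ICC 0.05, *b* = 0.5) gave a variance change of −0.6% at *G* = 0.2 (a slight loss) and a 4.9% reduction at *G* = 0.4.

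**5. Cost of the term.** Taking alpha 0.025 as two-sided and 42 communes, the critical *t* moves from 2.329 (40 df) to 2.331 (39 df).

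**The case against.** The best defence is that the documents lean towards enrolment first and that the plan already limits the damage. Entry is gated by CDR and Zarit thresholds. The adjusted models include dementia severity and NPI-Q severity, which overlap with the memory, behavioural and functional problems that local staff look for. The SAP also compares the arms at baseline, so gross differences in measured variables would show. All of this stands as mitigation. It does not cover unmeasured selection, and it does not replace a statement of when the arm is released.

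Three stronger readings are tempting, and the documents do not support them.

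- *That recruiters knew the arm.* No passage says so.
- *That later communes recruited with a known arm because recruitment runs for about three years.* This would need all communes to be randomised at the start, which is not stated; even then a list can be held back.
- *That the people who find cases also deliver the intervention.* The documents do not separate the roles, but an absence is not evidence of overlap.

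On district, the defence is largely right. The commune random intercept absorbs district variation, so leaving district out does not invalidate the test. The gap, slope, ICC and split are all assumed, and 22% is the chance of marked imbalance only under an even split.

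**Conclusion.** The point holds as an unstated safeguard. The protocol does not secure that a commune's arm is withheld until its caregivers are enrolled, and masking stops at the outcome assessors. This leaves a route to recruitment bias that the thresholds, covariates and baseline comparison reduce but do not close. No size or direction is claimed. If practice is already enrolment first, stating so in section 7 settles the matter.

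District is a minor matter of precision. Under the stated assumptions, stratification plus a district term removes roughly 1–9% of the variance of the arm contrast across splits from 21:21 to 10:32, or about 0.5–5% in standard error. It would not justify a change alone, but it is nearly free for communes still to be assigned. The recommendation rests mainly on the concealment wording: it should be added, and confidence in the point is medium.

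**What to change.** 1. **Concealment (protocol section 7).** State that each commune's caregivers are screened, consented and baseline-assessed, and its roster of 5–15 closed, before its allocation is released; that release is by an existing team member independent of the clinics and of recruitment; and that no caregiver is added afterwards. Baselines within a commune need not be done at the same time; each need only precede release.
2. **District (protocol section 7 and SAP).** For communes not yet assigned, stratify by district with a method that does not make late assignments guessable. Options are to randomise closed rosters in batches within district, or to use concealed varying block sizes. Include district as a fixed effect in the primary model.
3. **Only if some communes were released part-way through enrolment.** Record release and consent dates, and report a sensitivity analysis of caregivers who consented before release. For communes released before any enrolment that group is empty, so the analysis offers no check there.

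**Cost.** Wording in both documents, one existing person to hold the sequence, one degree of freedom, and no extra visits. Early enrollees wait for their roster to close and a few may be lost. September 2023 to March 2024 is 6 months, the full length of follow-up, so the last rosters must be closed and baseline-assessed by September 2023. Stratification cannot reach communes already assigned.

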## 8) Data and/or Specimen Management and Confidentiality

REDCap will be used to collect outcomes data. Procedures for maintenance and confidentiality include 1) assigning each participant a unique identifier, 2) data collected will be labeled using the unique identifier and will be stored separately from the key linking personal information (e.g. name, date of birth, address, phone number) and identifiers, 3) data will be kept on a secure server that is only accessible to research staff, 4) at the conclusion of the study, the key linking identifiers and personal information will be destroyed, 5) all research personnel in the U.S. who have access to the patient data will receive training on conducting human research (e.g. NIH online course) – all investigators in Vietnam will participate in the local equivalent of this training.

## 9) Data and/or Specimen Banking

- a) Will the data or specimens ever be used by you or other researchers to answer a different research aim that is not included in this study?  
 Yes - Complete the remainder of Section 9.  
 No - Do not complete Section 9. Go to section 10.
- b) What will be banked for future use?  
 De-identified data/specimens. Banked data/specimens cannot be linked to an individual.  
 Identifiable data/specimens – Banked data/specimens will include identifying information.  
 Coded data/specimens – Banked data/specimens will be stripped of identifiers and assigned a code. A key will be maintained that links the identifiers to the data/specimens.  
 Contact information will be banked for future research opportunities.
- c) Where will the data/specimens be banked?  
Computer files are password protected, and data are maintained on a secure firewall-protected network of the UC Davis Health System, REDCap.
- d) How long will the data/specimens be banked?  
After the study, the key linking personal identifiers to the survey data will be destroyed. De-identified data will be kept indefinitely.
- e) Who will have access to the banked data/specimens?  
Only select researchers involved in the project will have access to these data. Only de-identified data will be shared to other researchers who wish to access banked data.

PROTOCOL TITLE: Cluster Randomized Controlled Trial to Test the Efficacy of a Psychosocial Intervention (REACH VN) to Support Alzheimer's Family Caregivers in Vietnam

f) Describe the procedures to release data/specimens. Include the process to request a release, approvals required for release, who can obtain data/specimens, and the data/specimens to be provided.

- Recipient investigators who wish to access banked data will need to contact PIs ([name] and [name]) for an inquiry.
- If PIs agree for accessing banked data, the following approval steps will be taken:
  - + Recipient investigators will submit a proposal to PIs with the following information:
    - Title
    - Recipient PI's contact information and team members/co-authors
    - Introduction
    - Research questions
    - Data variables
    - Analysis plan
    - References
  - + Recipient investigators will submit an IRB approval letter from their local institution.
  - + PIs will submit the UC Davis Data Use Agreement request to UC Davis Innovation Access for recipient investigators to complete the Data Use Agreement Form.
  - + After recipient investigators receive approval documents, de-identified data will be transferred to them electronically through a password encrypted zip file.
- Recipient investigators are:
  - + required to safeguard data provided to them and ensure deletion/destruction of the data upon completion of their project
  - + restricted from attempting to identify participants using the data provided to them
  - + restricted from presenting data in any manner which could identify participants
  - + restricted from further distribution of the data.
  - + required to acknowledge the funding in any publication or presentation “Research reported in this publication was supported by the National Institute on Aging (NIA) of the National Institutes of Health (NIH) under award number R01AG064688 ([name]/[name] MPI). The content is solely the responsibility of the authors and does not necessarily represent the official views of the NIA and the NIH.”

PROTOCOL TITLE: Cluster Randomized Controlled Trial to Test the Efficacy of a Psychosocial Intervention (REACH VN) to Support Alzheimer's Family Caregivers in Vietnam

Note: Identifiable protected health information extracted from the UCDH EMR under an IRB-issued waiver of HIPAA Authorization may not be re-disclosed/released outside the study team.

## 10) Provisions to Monitor the Data to Ensure the Safety of Subjects

The goal of this cluster randomized controlled trial care is to assess the efficacy of the psychosocial intervention to support Alzheimer's family caregivers. Case review will occur on a weekly basis with a team that includes the care manager and the local PI and investigators from the UC Davis and UMN. The caregiver's level of distress and any indicators of elder abuse/neglect will be reviewed at each session.

This study will have a Safety Office (SO), who will meet 1-2 times each year to review the progress of the study, including adverse events, procedures for maintaining the confidentiality of data, and the quality of data collection, management, and analyses. The SO will also review any issues that arise in terms of conflict of interest or serious adverse events as needed. The SO will report directly to the funder (i.e., NIA).

[name] will be responsible for overall monitoring and appropriate reporting of adverse events including serious adverse events that occur during the study. Plans regarding reporting of adverse events will follow guidelines and policies of UC Davis as well as NIH. Adverse events will include events untoward or unfavorable mental or physical health-related occurrence in a human subject that is temporally associated with the subject's participation in the research, regardless of whether they are considered related to the subject's participation in the research. Examples of such events that might occur include incidents of brief hospitalization, caregiver distress or depression, instances of elder abuse or neglect, and other unanticipated events. Serious adverse events will be further defined as those events that seriously jeopardize the participant's health, including prolonged hospitalization, suicide attempts, and death. The overall goal of this plan is to have both serious adverse events (SAE) and non-serious adverse events (NSAE) that are viewed as likely (i.e., 50% or higher) related to study participation reported to both the UCD IRB and NIH in a timely fashion.

As a routine part of training, intervention study staff will be educated to monitor for these events and to report them to the research staff. Interventionists or other research staff will complete AE Field Report Form and provide this to Hai Duong project lead (i.e, [name]) within 48 hours. [name] will send all AE Field Report Forms to NGH RCT leads (i.e, [name] and [name]), and the interventionist supervisors within 48 hours. Upon receiving the report from [name], [name] must confirm that she has received the report and is available to act upon it. [name] will review AE Field Report Form, complete AE Form and, if it is a SAE,

PROTOCOL TITLE: Cluster Randomized Controlled Trial to Test the Efficacy of a Psychosocial Intervention (REACH VN) to Support Alzheimer's Family Caregivers in Vietnam

complete SAE Form and send to study PIs ([name], [name], and [name]) within 48 hours. [name] will serve as back-up in [name] is not available. Within 2 working days of receipt of the information about the SAE, [name] will share this information with the research team and the SO. If the SAE is viewed as likely (i.e., >50% probability) of being related to participation in the study, the SAE will be reported to the UCD IRB and to NIH within 2 working days of this determination with the goal of reporting all such events to UCD IRB and to the NIH PO within 5 working days of the time [name] became aware of the event. NSAE will be shared with the core members of the research team, including Drs. [name], [name] and [name], at their regular biweekly meetings. If NSAE are deemed as possibly related to study participation they will be reported to the SO within one week and, if the SO views them as "probably" (i.e., >50% likelihood) of being related to study participation, to the UCD IRB and NIH PO within 5 working days. All SAE and NSAE that are viewed as not likely to be related to research participation will be reported on an annual basis to the NIH PO as part of the progress report as well as to the institutional IRBs.

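### Serious adverse events share the first two 48-hour hand-offs with minor ones, so the PIs may first be told at 6 days; a parallel copy of the field form would cut that limit to 2

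*Protocol*

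**What the plan says.** The reporting chain is in Protocol section 10 (Provisions to Monitor the Data to Ensure the Safety of Subjects). Personal names are removed from the text available for review.

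- **Link 1.** Field staff fill in the AE Field Report Form and "provide this to Hai Duong project lead (i.e, [name]) within 48 hours".
- **Link 2.** That lead "will send all AE Field Report Forms to NGH RCT leads" "and the interventionist supervisors within 48 hours". This covers all forms and makes no distinction by seriousness.
- **Link 3.** An NGH lead reviews the field form, completes the AE Form and, for an SAE, must "complete SAE Form and send to study PIs ([name], [name], and [name]) within 48 hours".
- **To the SO.** "Within 2 working days of receipt of the information about the SAE", a named person shares it with the research team and the SO.
- **To the IRB and NIH.** An SAE judged likely related is reported within 2 working days of that judgement, "with the goal of reporting all such events to UCD IRB and to the NIH PO within 5 working days of the time" a named person became aware of the event. The judgement itself has no time limit.
- **Non-serious events.** "NSAE will be shared with the core members of the research team" at the regular biweekly meetings.

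The same section lists suicide attempts and death among SAEs. It also provides a weekly case review that includes the local PI and the US investigators. Section 12 mentions an emergency protocol for situations such as threats of self-harm. Neither of these sets a time for reporting an SAE.

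**The concern.** The field worker who first learns of a suicide attempt or death has no quicker route than for a trivial event. Seriousness first changes the handling at link 3, when the SAE Form is completed, and by then two 48-hour limits may already have been used. The stated goal of 5 working days may look like the overall ceiling. If it starts when a PI receives the SAE, however, it says nothing about the time before.

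What is at stake is oversight of participants, not the treatment comparison. A site that keeps every limit could leave the PIs uninformed for most of a week. The SO otherwise meets only once or twice a year, so this chain is the only timed route by which it learns of an SAE.

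**Working it through.** **Inputs, all from Protocol section 10**

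- L1 = L2 = L3 = 48 h, run in sequence. The start of L1 is not stated and is taken as staff awareness.
- S = 2 working days, from receipt of the SAE to sharing with the SO.
- D = time to judge relatedness. No limit is given; 0 or 1 working day is assumed.
- R = 2 working days, from that judgement to the IRB and NIH.
- Goal = 5 working days from a named person's awareness.

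Hour limits run in calendar time. Working days are Monday to Friday without holidays. All seven start weekdays were tried.

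**1. The plan's own figure.** From PI receipt, S + D + R = 2 + 0 + 2 = 4, or 2 + 1 + 2 = 5 working days. The 5-day goal is reproduced.

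**2. Time to the PIs.** L1 + L2 + L3 = 3 × 48 h = 144 h = 6 days. The NGH leads and supervisors have the form by 2 × 48 h = 96 h = day 4.

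**3. Time to the SO.** Two working days span 2 to 4 calendar days, depending on the weekday. If the person who informs the SO is a PI receiving on day 6: 6 + 2 = 8 to 6 + 4 = 10 calendar days.

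**4. Where the 5-day goal could start.** Depending on weekday, 48 h contains 0 to 2 working days, 96 h contains 2 to 4, and 144 h contains 4 to 5. Adding S + D + R = 4 to 5 gives the third column. The last column drops S, for the case where relatedness is judged while the SO is being informed (D + R = 2 to 3).

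| Clock starts at awareness of | Working days before PI receipt | To IRB/NIH, steps in sequence | To IRB/NIH, judgement in parallel |
|---|---|---|---|
| Field staff | 4–5 | 8–10 | 6–8 |
| Hai Duong lead | 2–4 | 6–9 | 4–7 |
| NGH lead | 0–2 | 4–7 | 2–5 |
| PI (receipt) | 0 | 4–5 | 2–3 |

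With every limit used in full, a start at field-staff awareness never fits within 5, and a start at PI receipt always does. In sequence, a start at the NGH lead fits for Thursday, Friday or Saturday starts when D = 0, and for Friday when D = 1.

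**5. What the goal leaves out.** Five working days span 5 to 7 calendar days. If the goal runs from PI receipt, a likely related SAE may reach the IRB and NIH at 6 + 5 = 11 to 6 + 7 = 13 calendar days after field awareness.

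**6. With a parallel copy inside the first 48 hours.** PIs: 48 h = 2 days. SO: 2 + (2 to 4) = 4 to 6 calendar days. IRB and NIH, with the goal unchanged: 2 + (5 to 7) = 7 to 9 calendar days.

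**The case against.** A fair defence has several parts.

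- **The limits are maxima.** Nothing stops staff from telephoning the same day, and weekly case review may bring a case to the investigators sooner. This stands, and the figures are upper limits only. But case review is not a timed SAE route, and the text does not list the SO among its members.
- **People able to act know earlier.** The NGH leads and supervisors have the report by day 4, and section 12 provides for emergencies. This also stands: reporting time is not response time, and one should not infer that an emergency goes unattended.
- **SAEs do split off from minor events.** A reader might infer that all three hand-offs are shared. The documents clearly support two. The third limit is most naturally read as attached to the SAE Form, since non-serious events go to biweekly meetings. The 6-day total does not change.
- **The 5-day goal is not contradictory.** A reader might infer that it conflicts with the steps, or that it must fail if it starts at the NGH lead. Neither is supported. Its start is stated and only the name is removed; from PI receipt the steps fit, and from the NGH lead they fit on some start days.
- **Institutional policy may be faster.** Section 10 says that reporting follows UC Davis and NIH policies, which cannot be checked here.
- **The risk is low.** The protocol classes the study as minimal risk, and section 12 reports no intervention-related SAEs in the pilot. This limits the weight of the point but does not remove a cheap improvement.

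**Conclusion.** The point holds as a design weakness that can be improved cheaply, not as an error or a contradiction. The protocol allows up to 6 days before the PIs are told of an SAE, including a suicide attempt or death, because the first two links treat all events alike. The SO may be told at 8 to 10 calendar days.

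The 6 days assume that the three limits run in sequence, that the first starts at staff awareness, and that no one at an earlier link is also a PI, which the removed names leave open. Time from the event to staff awareness has no limit and comes on top. The 8 to 10 days further assume no public holidays and that a PI informs the SO, which is plausible but an inference.

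It might seem to follow that the 5-day goal should be counted from the first staff member's awareness. The documents do not support that as a correction: it would be a new reporting standard, not a repair of inconsistent text. Nothing here affects the trial's estimates.

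**What to change.** Add a seriousness tick-box to the AE Field Report Form, worded from the SAE definition already in section 10. When it is ticked, field staff send that same form in parallel to the Hai Duong lead, the NGH leads and the PIs within the existing first 48-hour limit. The NGH lead completes the SAE Form afterwards. Non-serious events keep the present relay, and the 5-working-day goal keeps its present start.

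The cost is one tick-box, a distribution list and amended wording in section 10. The drawback is that the PIs will see some events that are later reclassified as non-serious.
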